10. EVALUATION OF EFFECTIVENESS

10.1. Scope of the effectiveness of the clinical trial

The effectiveness will be considered reached when a clinically relevant parameter in venipuncture is reached, section 10.2.1, and, whenever possible, an attempt will be made to reach the global effectiveness, section 10.2.

10.2. Global effectiveness reach

10.2. 1. Clinically relevant parameter in venipuncture

An optimal effectiveness for venipuncture at the first attempt will be considered reached when one of the three interventions manages to overcome the success rate at the first attempt through usual clinical practice. That is, when a success rate of more than 74% is achieved (55).

10.2.2. Clinically relevant parameter in pain

In the totality of the intravenous cannulations at the first attempt with any of the interventions, cases with moderate-moderate severe pain scores should be higher in cases of severe pain. That is, the scores from zero to six, included, must be greater than the scores from seven to ten, including (46).

10. 2. 3. Clinically relevant parameter in hemolysis.

In the basal samples, taken immediately after the application of any of the test arms, they should be less than 25 mg / dl (54). Concentrations will not be measured, but they must carry out a visual inspection and / or absorbance less than what corresponds, by means of bibliography, said cut-off point.

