6.2. Design and comparator

Experimental, randomized and controlled study with the usual technique of inserting a venipuncture catheter until now. Incomplete clinical trial, blind to third parties, in healthy volunteers, which consists of three arms, in which they are intervened and the comparator is applied.

Three interventions are established and a common comparator for all of them. Interventions:

1. Application of dry topical heat.
2. Application of high stagnation pressure.

3. Application of dry topical heat and high stagnation pressure. That is, the combination of the previous two.

Comparator:

1. Usual clinical practice, until now

Therefore, all individuals will be subjected to one of the three interventions and the comparator, whose sequence corresponds to the two periods established by the clinical trial of bioequivalence.

Therefore, all individuals will be subjected to one of the three interventions and the comparator, whose sequence corresponds to the two periods established by the clinical trial of bioequivalence.

It is understood that it is a crossover clinical trial because each subject is exposed to an intervention, and it is their own control; it is exposed to the comparator, whose purpose is to reduce the intraindividual variability and accentuate the effectiveness of the intervention per se. It is an incomplete crossing because it is not possible to subject each individual to the three interventions and it must be only one per random assignment. This impossibility could be supported by the low frequency of clinical trials of four periods carried out in the accessible environment.

In this way, any of the interventions assigned to it can be compared with the current procedure for antebrachial venous cannulation

6.3. Random assignment of interventions.

The intervention and the sequence of application of the intervention with the comparator will be randomly assigned.

They will be assigned with sealed envelopes where inside the corresponding intervention to be applied, the comparator and the corresponding sequence will be detailed. Emerging the following options:

1. CA-> C. Topical first period heat. Comparator in the second period.
2. C-> CA. Comparator in the first period. Topical heat in the second period.
3. P-> C. High pressure in the first period. Comparator in the second period.
4. C-> P. Comparator in the first period. High pressure in the second period.

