9.7. CLINICAL FINDINGS AND MATERIAL RESOURCES INVOLVED

9.7.1. Pain assessment

The evaluation of the pain will be carried out through the scale validated Visual Analog Scale (VAS) / numerical (45). Linear scale from zero to ten, from minimum pain to maximum perceived pain, escalating with integers in increasing order. The use of this scale is considered pertinent because it has been validated for the detection of both chronic and acute pain; through changes in temperature and for groups of individuals (45,46).

The individual will be provided with this scale, in paper format, so that he self-expresses the pain perceived in the venous cannulation with the randomly assigned method. It is provided immediately after the fixation of the vein catheter.

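### The pain parameter in section 10.2.2 uses no comparator and is met whenever fewer than half of the counted scores are 7 to 10, so it can be reached although an intervention raises severe pain well above usual practice

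*Combined protocol and SAP*

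**What the plan says.** Section 10.2.2 of the combined protocol and SAP defines the clinically relevant parameter for pain. The cannulations that count are described as "In the totality of the intravenous cannulations at the first attempt with any of the interventions", and the condition is that "the scores from zero to six, included, must be greater than the scores from seven to ten, including". No comparator value, difference, margin or test is named.

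The data behind it are described in section 9.7.1. The scale is a "Linear scale from zero to ten, from minimum pain to maximum perceived pain", in whole numbers, and the subject completes it "so that he self-expresses the pain perceived in the venous cannulation with the randomly assigned method". On timing, "It is provided immediately after the fixation of the vein catheter". Table 3 (section 9.7.3) lists the pain scale in both periods, and section 6.2 states that "all individuals will be subjected to one of the three interventions and the comparator". Each subject who completes both periods with a catheter fixed should therefore have one score under an intervention and one under usual practice.

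Three other places bear on the rule:
- Section 10.2.1, the venipuncture parameter, does have a reference. It is reached when an intervention "manages to overcome the success rate at the first attempt through usual clinical practice", set at 74%.
- Section 10.1 rests effectiveness on that venipuncture parameter; for the rest, "whenever possible, an attempt will be made to reach the global effectiveness, section 10.2".
- Section 14.3 plans a two-way ANOVA without interaction, with pain as the dependent variable, for the objective relating method, hemolysis and pain.

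**The concern.** A criterion for pain in a trial against usual practice should respond when an intervention hurts more than usual practice. This one looks only at the intervention scores and has a cut at one half, so a several-fold rise in severe pain can leave it satisfied. The crossover was chosen so that each subject is their own control, yet the rule sets that control aside.

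It also seems to select on the primary outcome. Cannulations at the first attempt most naturally means first-attempt successes. Section 9.8 argues that venipuncture pain falls as the number of attempts falls, so on the protocol's own reasoning the cannulations left out are the more painful ones.

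At stake is a statement in the trial report that the pain parameter was reached, which readers would take as reassurance that the interventions do not make cannulation more painful.

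**Working it through.** **No figure to reproduce.** Section 10.2.2 gives no sample size, error rate, margin or reference rate. What can be checked is how often the rule is met for a given true rate of severe pain.

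**Inputs.**
- Severe means a score of 7 to 10 (section 10.2.2).
- Subjects: 54 (section 2.13), so 54/3 = 18 per intervention. As a check, 60 randomised (sections 6.3 and 14.1.2), so 60/3 = 20.
- Success at the first attempt: 74% with usual practice, 95% targeted (section 14.1.2).
- Severe-pain rate under usual practice: not in the documents. Values of 5% to 10% are assumed for illustration and enter only where stated.

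**Formula.** Let X be the number of severe scores among n counted cannulations and q the true severe rate. The rule is met when X < n − X, that is X < n/2. With X ~ Binomial(n, q), P(met) = P(X ≤ k), where k is the largest integer below n/2.

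**Per intervention and pooled.**

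| n | Largest severe count that passes | q = 20% | q = 30% | q = 40% | q = 45% | q = 60% |
|---|---|---|---|---|---|---|
| 18 | 8 (44.4%) | 0.996 | 0.940 | 0.737 | 0.578 | 0.135 |
| 20 | 9 (45.0%) | 0.997 | 0.952 | 0.755 | 0.591 | 0.127 |
| 54 | 26 (48.1%) | 1.000 | 0.998 | 0.912 | 0.727 | 0.052 |

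These figures count every subject. If only first-attempt successes count, n is smaller; with n = 13 the probabilities are 0.938 at 30% and 0.771 at 40%, so the picture is the same. A rise from an assumed 5–10% to 30% (three to six times) would pass about 94% of the time or more.

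**Pooled, with one bad arm.** The wording of section 10.2.2 allows the three interventions to be counted together. Suppose one arm of 18 has 100% severe scores. The rule is met if the other 36 subjects contribute at most 26 − 18 = 8 severe scores. With q = 10% in those two arms, P(Binomial(36, 0.10) ≤ 8) = 0.992; with q = 5% it is 0.9999.

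**First-attempt restriction.** At 74% success, 18 × 0.74 = 13.3, so about 13 count and 5 do not. The rule passes with 6 severe among 13. If all 5 excluded subjects had severe pain, (6 + 5)/18 = 61% of the arm would be severe with the rule still met. At the 95% target, 18 × 0.95 = 17.1, so only about 1 is excluded and the extreme is (8 + 1)/18 = 50%.

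**The case against.** Four points on the other side carry weight.

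- **Decision weight.** Section 10.1 lets effectiveness be declared on venipuncture alone. The pain rule cannot overturn that, so a reader who inferred that it decides the trial would be wrong.
- **Pain is compared elsewhere.** It is tempting to infer that the trial never sets pain under the interventions against usual practice. The documents do not support that: scores are taken in both periods and section 14.3 plans an ANOVA of pain across methods. That analysis is not described as paired, has no margin and is not tied to section 10.2.2, so the ANOVA could show more pain with an intervention while the parameter is still declared reached.
- **The rule is not empty.** A reader might infer that it passes for almost any result. Applied per intervention, it does not: at 60% severe it is met only about 13% of the time. Its weakness is below one half, and in the pooled reading.
- **An absolute floor may be intended.** Section 10.2.2 can be read as an acceptability limit, like the fixed hemolysis limit in section 10.2.3. That is a legitimate aim, but it does not show that pain is no worse than usual practice, and the adjoining venipuncture rule does use a reference.

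Two uncertainties also stand. The text does not say outright that only first-attempt successes count, and at the 95% target that restriction removes very little.

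**Conclusion.** The point holds as a defect of the rule in section 10.2.2, not of the trial's main conclusion. Followed as written, the rule can declare the pain parameter reached when severe pain is far more common with an intervention than with usual practice: probability 0.94 to 0.998 at a 30% severe rate and 0.74 to 0.91 at 40%, for 18 per arm and 54 pooled respectively. In the pooled reading it can also hide an arm in which every score is severe.

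The pass probabilities rest on independent scores with a common rate in each group and on full counts of 18 or 54. They do not depend on the unknown rate under usual practice, because the rule does not use it; only the size of the increase and the 0.992 figure use assumed rates of 5–10%. It should be changed, since paired data that answer the question are already planned.

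**What to change.** Base section 10.2.2 on the within-subject comparison with the comparator, separately for each intervention and over all cannulations with a pain score, whatever the attempt number. Report the paired difference in pain score and the paired difference in the proportion scoring 7 to 10, each with a 95% confidence interval.

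If a yes/no criterion is kept, judge the confidence interval against a margin the sponsor prespecifies. Requiring only that the observed severe proportion be no higher than with the comparator would be a poor substitute. With no true difference, 10% severe under both methods and paired scores treated as independent, it would fail by chance about 39% of the time at n = 18 and 44% at n = 54.

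State how subjects with no catheter fixed are handled. Section 9.7.1 gives the scale after fixation, while section 7.4 keeps second-period subjects in whom cannulation was tried but not achieved. Say also how this analysis relates to the ANOVA in section 14.3.

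The cost is SAP wording and one paired analysis of data already planned. The downside is a criterion that is harder to meet and wide intervals. For the severe proportion at 18 per arm, under the same 10% and independence assumptions, the half-width is about 1.96 × √(2 × 0.10 × 0.90/18) = 0.196, or roughly 20 percentage points.

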11. SAFETY ASSESSMENT

11.2. Safety monitoring

11.2.1. Record adverse events

A record of the secondary events and the symptomatic and specific adverse reactions will be carried out, which will be assessed by visual inspection. It will be the nurses, who apply each arm, those responsible for the visual inspection and the communication of the adverse reaction, if any, to the principal investigator and / or collaborating researcher. Both the principal investigator, the collaborating researcher and the collaborating nurses will be able to record any secondary effect (9).

The definition of adverse reactions requires adaptation to medical devices. Its calving is considered from the application of any intervention and / or comparator. There will be an approximation of the causality between the effect and the applied method; according to what the World Health Organization establishes (WHO) (56):

1. Certain
2. Probable.
3. Possible.
4. Unlikely
5. Conditional / Not classified
6. Not evaluable / Unclassifiable

Likewise, the severity will be recorded; according to the WHO (57), with modification:

1. Serious
2. Moderate.
3. Mild.
4. Incidental.

The frequency of appearance thereof will be calculated according to what is established by the Council for International Organizations of Medical Sciences (CIOMS) (58):

1. Very common: They occur with a frequency greater than or equal to 1 case every 10 patients.
2. Frequent: They occur with a frequency greater than or equal to 1/100 but less than 1/10.
3. Uncommon: They occur with a frequency greater than or equal to 1 / 1,000 but less than 1/100.
4. Rare: They occur with a frequency greater than or equal to 1 / 10,000 but less than 1/1000.
5. Very rare: They occur with a frequency less than 1 / 10,000.

Each case will be followed until it ceases, and the method used to remit said effect will be registered.

The appearance of local erythema has been registered as an adverse effect of dry topical heat (37). Likewise, the appearance of a hematoma due to traumatic puncture is expected.

It is considered that the registration of side effects in this trial could be justified as one of the objectives of clinical research with medical devices, both under the conditions of use for which they have been accredited and for those that have not yet been . In this way, it is intended to increase the knowledge about the possible risks, and that these do not exceed the benefits, as well as the feasibility of the implementation thereof for the intended use in the present clinical trial (9).

11.2.2. Serious and unexpected adverse events

No serious and unexpected adverse reactions are anticipated with the medical devices used in this trial. However, if they were produced, they would be registered in the same manner as for the adverse events and their notification would proceed; Section 11.2.3.

11.2.3. Serious and unexpected adverse events notification

The notification will be carried out early and in the shortest possible time from the appearance of said reaction. The responsibility for the notification rests with the principal investigator. The principal investigator of the clinical trial of bioequivalence, the Clinical Research Ethics Committee with medicines and medical devices (CEIm) involved, and the Spanish Agency for Medicines and Health Products (AEMPS), the department of health products involved, will be notified

The notification to the AEMPS of the Serious and unexpected adverse events will be carried out as established by the AEMPS in the national environment. It will be done in Spanish, notifying through the FEDRA portal; when you get access to it.

In case of impediment in accessing said portal, it will be sent by fax, to the number ([contact], or, through CD / DVD with postal mail, enclosing the accompanying letter and validated forms destined for such use ; available in your guide (59).

In addition, it is intended to notify the Serious and unexpected adverse events in Eudravigilance-CT.

11.2.4. Monitoring of adverse events and / or serious and unexpected events.

The follow-up will be carried out in person and, if this is not possible, by telephone or via e-mail. Likewise, the time of follow-up is not established and will be the time necessary until it ceases, it will be the effect itself that marks the temporality.

12. ETHICAL AND ECONOMICAL ASPECTS**12.1. Ethical aspects****12.1.1. Legal framework of the trial**

The ethical, methodological and protection principles of the subjects of this study are governed by the provisions of Royal Decree 1090/2015, of December 4, which regulates clinical trials with medicines, the Ethics Committees of the research with medicines and the Spanish Registry of Clinical Studies through which the rights of respect, beneficence, non-maleficence and justice prevail over any other interest (2). In the same way, all the principles contemplated in the Declaration of Helsinki (60), applicable to nursing research and competence, will be safeguarded.

The present clinical trial could be considered as a low intervention level, according to the definition established for this type of tests by Royal Decree 1090/2015 (2).

Likewise, the medical devices used in this study are considered active according to Royal Decree 1616/2009, of October 26, which regulates active implantable medical devices. (9).

12.1.2. Notification to entities and committees

According to the provisions of the AEMPS and current legislation, the need for notification of the existence and intention to carry out the present clinical trial to the AEMPS is foreseen, provided that the favorable opinion of a CEIm has been previously obtained (2 , 9,12). Likewise, the request for exemption from fees is envisaged, since it is an independent investigation of an academic nature.

The non-issuance of an AEMPS approval is considered justified because this study is considered a low-level intervention clinical trial, in which all medical devices are commercialized. Both are considered class IIa according to the classification of the AEMPS and, although in the case of seed bags do not show the CE mark which could justify their clinical research, they will be used for a different purpose than the accredited one. However, its application will be carried out according to the instructions for use described for the purposes that are accredited for each medical device involved in the study.

12.1.3. General rules for collaborating researchers

All the personnel involved in the collaboration of this clinical trial have a certificate of Good Clinical Practices (GCP) in force; less than two years old. In this way, the acceptance of the data presented is facilitated, derived from the compliance of this protocol. This is how the quality standards and the guidelines of the International Conference on Harmonization (ICH) on good clinical practice are assumed (2). In addition, it is ensured, by means of a register, that all the components of the equipment work in a harmonized manner according to the Standardized Work Procedures of the UECHUP.

12.1.4. Information sheet and informed consent

First, the individual will be informed of the intervention as verbal communication as written through the information sheet. You will need to write your name, date of birth and the name of the professional who has explained the information in the informed consent in your handwriting. Subsequently, the signature and date of the agreement of the subject, as well as of the principal investigator before it, will be collected and an original copy of both the information sheet and the informed consent will be provided; APPENDIX I.

It was considered appropriate to draw up a box corresponding to the evaluation of hemolysis. It is considered that it could be justified because blood extractions are not required in addition to those already stipulated, manipulation of the peripheral venous accesses is not affected more than expected, two microliters would be collected in at most in each sample; Finally, his analysis has no connection with genetic data or any other personal data. In addition, your evaluation will be blind (61).

The subject will be able to ask all the questions that he considers pertinent and will be answered, likewise, he can revoke his agreement at any time, without negative consequences and without the need to provide a justified reason. No procedure will be carried out if the compliance duly completed by each subject has not been collected.

12.1.5. Confidentiality access to information.

The protection of the data of the participants, whether personal or health related, will be kept coded, with two digits, in a reversible manner, by means of the document prepared which will only be accessed by the sponsor, principal investigator and collaborating researcher in the trial. Said file will be confidential and will not leave the institution where it has been collected,

UECHUP. In this way it is intended to address the security of data as established in Organic Law 15/1999, of December 13, on the Protection of Personal Data (62).

The data will be collected in paper format and a collection record form (CRF) will be created. The code will be dissociated with the personal data of each individual in a reversible manner until the end of his admission or refer the adverse effect; in which case.

The coded and, later, anonymized data will only be used to check the sample count and that no subject is lost in the transcription of the information to the statistical database SPSS version 23 for further statistical analysis. Only the principal investigator will have access, in the first instance, to avoid altering the data processing and controlling access to it (62).

All collected data are subject to professional secrecy during and after the investigation, as well as to its storage, safeguarding the integrity and readability of the data during, at least twenty-five years after the end of the study (2.62). If there is an inspection in some cases, they will have access to the data, as long as they maintain professional secrecy, as established in Organic Law 15/1999, of December 13, on the Protection of Personal Data (62).

12.2. Economical concerns

12.2.1. Insurance

As a result of being a low-level intervention clinical trial, the attributable risks are considered minimal compared with those of the usual clinical practice and according to what is established for them by Royal Decree 1090/2015 (2) in Chapter III Article nine of compensation for damages, it is considered that the specific insurance contract for the present trial is not necessary and that it could be supported by the clinical bioequivalence trial insurance in which this protocol is applied.

